9.1.9. Protocol Compliance

The investigator is responsible for ensuring the study is conducted in accordance with the procedures and evaluations described in this protocol.

9.2. Sponsor Responsibilities

9.2.1. Protocol Modifications

Protocol modifications, except those intended to reduce immediate risk to study participants, may be made only by Gilead. The investigator must submit all protocol modifications to Gilead in accordance with local requirements and receive documented approval before modifications can be implemented.

9.2.2. Study Report and Publications

A clinical study report will be prepared and provided to the regulatory agency when applicable and in accordance with local regulatory requirements. Gilead will ensure that the report meets the standards set out in the ICH Guideline for Structure and Content of Clinical Study Reports (ICH E3). Note that an abbreviated report may be prepared in certain cases. Investigators in this study may communicate, orally present, or publish in scientific journals or other scholarly media in accordance with the Gilead clinical trial agreement.

9.3. Joint Investigator/Sponsor Responsibilities

9.3.1. Payment Reporting

Investigators and their study staff may be asked to provide services performed under this protocol (eg, attendance at investigator meetings). If required under the applicable statutory and regulatory requirements, Gilead will capture and disclose to federal and state agencies any expenses paid or reimbursed for such services, including any clinical study payments, meal, travel expenses or reimbursements, consulting fees, and any other transfer of value.

9.3.2. Access to Information for Monitoring

The monitor is responsible for routine review of the CRF/eCRF at regular intervals throughout the study to verify adherence to the protocol and the completeness, consistency, and accuracy of the data being entered on them. The monitor should have access to any participant records needed to verify the entries in the CRF/eCRF. The investigator agrees to cooperate with the monitor to ensure that any problems detected through any type of monitoring (central, on site) are resolved.

9.3.3. Access to Information for Auditing or Inspections

Representatives of regulatory authorities or Gilead may conduct inspections or audits of the clinical study. If the investigator is notified of an inspection by a regulatory authority, the investigator agrees to notify the Gilead medical monitor immediately. The investigator agrees to provide to representatives of a regulatory agency or Gilead access to records, facilities, and personnel for the effective conduct of any inspection or audit.

9.3.4. Study Discontinuation

Gilead reserves the right to terminate the study at any time, and the investigator has the right to terminate the study at his or her site. Should this be necessary, both parties will arrange discontinuation procedures and notify the participants, appropriate regulatory authority, IRBs, and IECs. In terminating the study, Gilead and the investigator will ensure that adequate consideration is given to the protection of the participants' interests.

Appendix 2a. Study Procedures Table

Visit ^c	Screening ^d	P1												P2 ^a												P3 a,b	P4 a,b			
		Day -13/Prebaseline	VES Dose1-Day 0/Baseline	Day 1	Day 2	Day 8	Day 9	VES Dose 2-Day 14	Day 21	VES Dose 3-Day 28 ^e	Day 35	VES Dose 4-Day 42	Day 49	VES Dose 5-Day 56	Day 57	VES Dose 6-Day 70	Day 63	VES Dose 7-Day 84	Day 77	VES Dose 8-Day 98	Day 105	VES Dose 9-Day 112	Day 119	VES Dose 10-Day 126	Day 127	Day 128	Day 133			
Informed consent	X																													
Medical history	X ⁱ	X																												
AE and Con Med	X	X	X	X	X	X	X	X	X	X	X	X	X	X	X	X	X	X	X	X	X	X	X	X	X	X				
Complete physical exam	X																													
Symptom-directed physical exam		X	X	X	X	X	X	X	X	X	X	X	X	X	X	X	X	X	X	X	X	X	X	X	X	X				
12-Lead ECG	X																										X	X		
Vital signs ^l	X		X	X		X		X		X		X		X		X		X		X		X		X		X ^j	X ^k	X	X	
Body weight	X	X	X	X	X	X	X	X	X	X		X		X		X		X		X		X		X		X ^j	X ^k	X	X	
Height	X																													
Review of I/E criteria		X																												
Urinalysis	X	X	X	X	X	X		X	X	X		X		X		X		X		X		X		X		X ^j	X ^k	X	X	
Urine pregnancy test ^m		X	X									X		X			X			X			X			X ^j	X ^k	X	X	
Chemistry ⁿ	X	X	X ^o	X	X	X		X	X	X		X		X		X		X		X		X		X		X ^j	X ^k	X	X	
Hematology ^p	X	X	X ^o	X	X	X		X	X	X		X		X		X		X		X		X		X		X ^j	X ^k	X	X	
Metabolic assessment ^q	X																													
Creatinine clearance ^r	X	X	X	X	X	X		X	X	X		X		X		X		X		X		X		X		X ^j	X ^k	X	X	
Follicle-stimulating hormone ^s	X																													

Visit ^c	Screening ^d	P1												P2 ^a												P3 ^{a,b}	P4 ^{a,b}	ESDD ^b			
		Day -13/Prebaseline	VES Dose1-Day 0/Baseline	Day 1	Day 2	VRC & CAP Dose-Day 7	Day 8	Day 9	VES Dose 2-Day 14	Day 21	VES Dose 3-Day 28 ^e	Day 35	VES Dose 4-Day 42	Day 49	VES Dose 5-Day 56	Day 57	VES Dose 6-Day 70	Day 63	VES Dose 7-Day 84	Day 77	VES Dose 8-Day 98	Day 91	VES Dose 9-Day 112	Day 105	VES Dose 10-Day 126	Day 119	VES Dose 11-Day 133	Day 133	Day 134-336	End-of-Period 3 Visit ^f	Day 337-413
Whole blood ISG mRNA panel	X X ^o	X	X ^o	X										X X															X	X X	X X
HIV-specific antibody profiling using plasma	X X ^o					X																									
HIV staging ^{ff}	X																														
Serum pregnancy test ^{gm}	X																														
CD4+ and CD8+ T cell absolute count, percentage, and CD4/CD8 ratio	X	X ^o					X	X	X	X	X	X	X						X	X	X	X	X	X	X	X	X ^j	X X ^k	X X		
HBV/HCV serology ^l	X																														
VES PK ^u			X	X	X																										
Serum VRC07-523LS & CAP256V2LS PK ^v						X X	X X	X X	X X					X			X		X							X X		X X			
Plasma dolutegravir PK ^w														X			X		X		X						X X		X X		
Plasma HIV-1 RNA ^x	X X	X ^o			X		X X	X X	X	X	X	X	X	X	X	X	X	X	X	X	X	X	X	X	X X	X X	X X	X X			
Plasma HIV-1 resistance testing to VRC07-523LS, CAP256V2LS, and baseline ART		X ^o			X		X X	X X	X	X	X	X	X	X	X	X	X	X	X	X	X	X	X	X X	X X	X X	X X	X X			
Plasma for active HIV-1 reservoir	X X ^o	X	X ^o	X X										X X													X X		X X		
Soluble proteins in the TruCulture® Whole Blood Culture System	X																														

Visit ^c	Screening ^d	P1												P2 ^a												P3 ^{a,b}	P4 ^{a,b}	ESDD ^b		
		Day -13/Prebaseline	VES Dose1-Day 0/Baseline	Day 1	Day 2	VRC & CAP Dose-Day 7	Day 8	Day 9	VES Dose 2-Day 14	Day 21	VES Dose 3-Day 28 ^e	Day 35	VES Dose 4-Day 42	Day 49	VES Dose 5-Day 56	Day 57	VES Dose 6-Day 70	Day 63	VES Dose 7-Day 84	Day 77	VES Dose 8-Day 98	Day 105	VES Dose 9-Day 112	Day 119	VES Dose 10-Day 126	Day 127	Day 128	Day 133	Day 134-336	End-of-Period 3 Visit ^f
Soluble proteins (cytokines, chemokines, and inflammatory markers)	X	X ^o	X			X								X	X	X														
PBMC sample for testing of viral sensitivity to the VRC07-523LS and CAP256V2LS mAbs	X ^y																													
PBMC HIV-specific T cell responses	X					X											X													
PBMC immune cell frequency, activation and phenotyping	X	X ^o	X			X								X	X	X														
PBMC latent HIV-1 reservoir	X																													
PBMC active HIV-1 reservoir	X	X ^o	X	X										X	X															

Visit ^c	Screening ^d	P1														P2 ^a														P3 ^{a,b}	P4 ^{a,b}	ESD ^b
		Day -13/Prebaseline	Day 1	Day 2	VRC & CAP Dose-Day 7	Day 8	Day 9	VES Dose 2-Day 14	Day 21	VES Dose 3-Day 28 ^e	Day 35	VES Dose 4-Day 42	Day 49	VES Dose 5-Day 56	Day 57	VES Dose 6-Day 70	Day 63	VES Dose 7-Day 84	Day 77	VES Dose 8-Day 98	Day 105	VES Dose 9-Day 112	Day 119	VES Dose 10-Day 126	Day 127	VES Dose 11-Day 133	Day 134-336					
Anti-VRC07-523LS and anti-CAP256V2LS antibody profiling from serum ^{aa}	X									X		X		X		X		X		X		X		X		X		X ^{bb}	X ^c			
Review of ongoing eligibility check prior to study dosing		X		X		X		X		X		X		X		X		X		X		X		X		X						
Birth control check	X	X	X	X	X	X	X	X	X	X	X	X	X	X	X	X	X	X	X	X	X	X	X	X	X	X	X	X				
Participant agreement to follow study contraceptive requirements	X																															
In-clinic dosing		X			X			X		X ^{gg}		X ^{hh}		X ^{hh}		X ^{hh}		X ^{hh}														

- e At the Day 28 visit and prior to the Period 2 Day 35 visit, participants will be assessed to determine whether the criteria necessary to begin ATI are met. All of the following criteria must be met for a participant to begin ATI: Viral load < 50 copies/mL; CD4+ T cell count > 400 cells/ μ L; negative urine pregnancy test; participant has received VRC07-523LS, CAP256V2LS, and at least 3 of the 10 scheduled doses of VES. Participant confirms agreement to request their partners to use condoms throughout the ATI period. The initiation of ATI (Period 2) may be postponed for up to 4 weeks after the last VES dose for participants to meet these requirements.
- f Participants who complete Period 3 or meet the ART restart criteria will be required to complete an end-of-Period 3 visit 1 week after their last visit.
- g End-of-study visit will occur 7 days (\pm 3 days) after completion of the final Period 4 visit.
- h ESDD visit is required for participants who prematurely discontinue study drug prior to completing the infusions of the VRC07-523LS and CAP256V2LS, or all 10 doses of VES, as described in Section 6.9.1, will complete an ESDD visit within 3 days of informing the investigator/site.
- i Medical history including route and estimated duration of HIV-1 infection, history of HIV-1 disease-related events, ART history for at least 12 consecutive months prior to screening, and prior concomitant medications within 35 days of the screening visit.
- j Day 147 and at each visit every 4 weeks thereafter

- k Day 343 and at each visit every 4 weeks thereafter
- l Vital signs (blood pressure, pulse, respiration rate, oxygen saturation, and temperature) will be monitored on dosing days at the following time points: (1) VES Dose 1 on baseline/Day 0, at predose, then at 1, 2, 4, 8, 12, 18, and 24 hours (Day 1) postdose (2) VRC07-523LS and CAP256V2LS infusion, and remaining VES Doses 2 to 10 at predose, then at 1, 2, 4, and 8 hours postdose.
- m Females of childbearing potential only. Positive urine pregnancy tests will be confirmed with a serum test.
- n Alkaline phosphatase, aspartate aminotransferase, alanine aminotransferase, total bilirubin, direct and indirect bilirubin, total protein, albumin, creatine kinase, bicarbonate, blood urea nitrogen, calcium, chloride, creatinine, glucose, phosphorus, magnesium, potassium, sodium, uric acid.
- o Sample to be taken before VES dosing.
- p Complete blood count with differential and platelet count.
- q Fasting (no food or drinks, except water, at least 8 hours prior to blood collection) glucose and lipid panel (total cholesterol, high-density lipoprotein, direct low-density lipoprotein, triglycerides). If the participant has not fasted prior to the visit, the visit may proceed, but the participant must return within 72 hours in a fasted state to draw blood for the metabolic assessments.
- r Creatinine clearance according to the Cockcroft-Gault formula: Female Estimated Creatinine Clearance = $[(140 - \text{age in years}) \times (\text{weight in kg})] / [72 \times (\text{serum creatinine in mg/dL})] \times 0.85$.
- s Serum follicle-stimulating hormone test is required for female participants < 54 years old who have stopped menstruating for ≥ 12 months, but are not permanently sterile or do not have documentation of ovarian hormonal failure.
- t Hepatitis B virus blood panel will be performed at screening (hepatitis B virus surface antigen, hepatitis B virus surface antibody, and hepatitis B virus core antibody). Hepatitis C antibody will also be performed.
- u PK samples for VES will be collected at predose (≤ 5 minutes prior to dosing), 1, 2, 4, 8, 12, 24 (Day 1), and 48 hours (Day 2) after the first dose.
- v Serum VRC07-523LS and CAP256V2LS PK collection on Day 7, at 0 hours (predose), end of infusion, 1, 2, 4, and 8 hours after end of infusion, and then at Days 8, 9, 14, 21, 28, 56, 84, 112, 133, 161, 189, 217, 245, 273, 301, 329, 343, 371, and 413.
- w Plasma dolutegravir PK collections will be obtained at: Days 56, 84, 112, 133, 161, 189, 217, 245, 273, 301, 329, and for participants in Period 4B PK collections at Days 343, 371, and 413.
- x From Period 2, if a confirmed rebound of HIV-1 RNA viral load ≥ 50 copies/mL occurs, the test should be completed weekly.
- y Only if not previously conducted.
- z Only at Day 147 visit.
- aa Blood samples anti-VRC07-523LS and anti-CAP256V2LS antibody profiling from serum will be collected at the following timepoints: prebaseline/Day -13, Days 28, 56, 84, 112, 133, 161, 189, 217, 245, 273, 301, 329, 343, 371, and 413.
- bb Days 161, 189, 217, 245, 273, 301, and 329 only.
- cc Days 343, 371 and 413 only.
- dd Lymph node and GALT biopsy will be collected from participants who provide additional consent at prebaseline/Day -13, Week 21 (beginning of Period 3), end-of-Period 3 visit, and the end-of-study visit. The samples can be collected within a window of ± 5 days.
- ee Only at Day 134 visit.
- ff Obtain HIV staging at detection using standard markers (eg, HIV-1 RNA, p24 antigen, fourth generation combination antigen/antibody enzyme-linked immunosorbent assay, HIV-1 Western blot), duration of viremia during acute HIV infection and peak HIV RNA
- gg For Dose 3 only, 6 mg [3x2 mg tablets] or 8 mg [4x2 mg tablets]) will be administered per discussion with and approval from the Gilead medical monitor based on safety and tolerability of prior doses.
- hh For Doses 4 to 10, 6 mg [3x2 mg tablets] or 8 mg [4x2 mg tablets]) will be administered per discussion with and approval from the Gilead medical monitor based on safety and tolerability of prior doses.

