1.4. Rationale for Dose Selection

1.4.1. Rationale for Dose Selection of Vesatolimod

Dose selection for VES is supported by the available PK, safety, and PD data from the completed Study GS-US-382-1450 and Study GS-US-382-3961 in ART-suppressed PWH, as well as the completed Study GS-US-243-0101 in healthy volunteers (for further information, please refer to the VES IB). The results from these studies indicate that VES is generally well tolerated up to 12 mg administered as a single dose or multiple doses, given every 2 weeks. As a TLR7 agonist, VES is expected to activate its receptor on plasmacytoid dendritic cells or B cells and stimulate the production of cytokines. Therefore, AEs related to influenza-like symptoms may be expected. When administered alone in ART-suppressed PWH and in healthy volunteers, VES up to 8 mg is well tolerated, with mild and infrequent influenza-like AEs (eg, fatigue, headache), whereas individuals receiving VES at the 10 mg dose or higher more frequently experienced influenza-like AEs. The VES starting dose selected for this study is 6 mg, with the option for intraparticipant dose escalation to 8 mg at the third VES administration (Day 28), pending safety and tolerability of the 6 mg dose in each participant, with close safety monitoring. Participants who escalate to 8 mg VES may remain on 8 mg VES, or de-escalate to 6 mg VES, pending safety and tolerability of the 8 mg VES dose in that participant. Participants who de-escalate to 6 mg VES would remain on 6 mg VES for the remainder of the study. The proposed dose range of 6 mg to 8 mg VES is expected to provide exposures associated with activity, as evidenced by induction of ISGs and cellular activation observed at VES doses of 4 to 12 mg.

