1.5. Risk/Benefit Assessment for the Study

Based on the current available clinical data, potential risks associated with VES include transient influenza-like symptoms, such as chills, pyrexia, aches, and headache and CRS. In completed and ongoing studies of VES, the majority of the influenza-like symptoms have been mild and transient. One healthy volunteer who received 1 dose of VES 8 mg coadministered with EVM 250 mg experienced a Grade 3 SAE of CRS that was considered related to VES, leading to treatment and observation in the hospital followed by full recovery (Section [1.2.1](#)). The other 3 participants receiving this regimen did not experience SAEs. Co-administration of EVM and VES 6 mg was generally safe and well tolerated in virologically-suppressed people with HIV-1 on ART. In this study, VES will not be coadministered on the same day as VRC07-523LS and CAP256V2LS, but rather separated by at least 7 days. Furthermore, these antibodies are not known to have off-target binding and have not been engineered with the same Fc-enhancement mutations as EVM, further lowering the risk of toxicity. There is no known or expected overlapping safety risk with VES, VRC07-523LS, and CAP256V2LS. However, it is possible that administration of VES in the presence of detectable plasma concentrations of VRC07-523LS and CAP256V2LS may transiently increase the risk of inflammatory events (see below). Additionally, as VES-related AEs are more common following Doses 1 and 2, enhanced monitoring after the first 2 doses of VES is proposed with adaptive monitoring thereafter. Participants will be monitored on site following study drug administration, and an external data monitoring committee (DMC) will evaluate safety data after the first 5 participants have reached Day 21. Nonclinical studies have reported findings of thrombocytopenia, hematologic effects, and hepatic injury. Hematologic effects or hepatic injury have not been observed in clinical studies. At the 12 mg dose level of VES in healthy volunteers (Study GS-US-243-0101), nongraded nonclinically significant decreases in platelet counts were observed in some participants, which resolved within 2 days without intervention. Treatment-emergent platelet decreases have not been observed at doses up to 12 mg in PWH in Study GS-US-382-1450 or in Study GS-US-382-3961. Safety laboratory values, including complete blood count and chemistry panels, will be regularly monitored throughout the study.

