5.3. Dosage and Administration

On dosing days, VES (6 mg [3 × 2 mg tablets] for Doses 1 and 2; 6 mg [3 × 2 mg tablets] or 8 mg [4 × 2 mg tablets] for Doses 3-10 per discussion with and approval from the Gilead medical monitor based on safety and tolerability of prior doses) should be administered orally by a participant with approximately 240 mL of water on an empty stomach (ie, no food or liquids except water for at least 2 hours prior to dosing; overnight fasting is preferable). Participants will not be allowed to consume water 1 hour before and 2 hours after dosing, except for the 240 mL administered with VES. Participants should remain fasted without food until 2 hours after dosing. Participants will be asked to provide information on food consumption and total fasting time prior to dosing.

There are no fasting requirements on VRC07-523LS and CAP256V2LS dosing days:

- VRC07-523LS, 20 mg/kg, IV infusion over 30 minutes
- CAP256V2LS, 20 mg/kg, IV infusion over 30 minutes

Supportive medications, including but not limited to antihistamines (such as diphenhydramine), acetaminophen (paracetamol), and steroids, will be available in the clinic settings during the IV infusions.

Study drug infusion may be slowed and/or discontinued if an infusion-related adverse reaction occurs. Symptom severity will be evaluated, and supportive medications will be provided as clinically indicated. Study drug infusion may be resumed upon symptom resolution. If the symptoms, in the judgment of the investigator and the medical monitor, compromise the ability to continue study-specific procedures or are considered to not be in the participant's best interests, the infusion will be permanently discontinued.

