6.2.3. Treatment Assignment

Obtain participant number and assign treatment to the participant in the IWRS. The participant number assignment and treatment assignment will be performed in clinic at the baseline/Day 0 visit, provided that all screening procedures have been completed and participant eligibility has been confirmed.

If a participant's ART regimen is changed \leq 45 days prior to prebaseline/Day -13, plasma HIV-1 RNA $<$ 50 copies/mL at prebaseline/Day -13 visit is required to confirm eligibility. Once a participant number has been assigned, it will not be reassigned to any other participant.

6.3. Treatment Assessments—Period 1

Participants will have up to 9 visits over 4 weeks. Dosing of VRC07-523LS and CAP256V2LS will occur in a sequential regimen with VES.

Doses 1 to 3 of VES will be administered orally on baseline/Day 0, Day 14, and Day 28. For Dose 3 only, 6 mg [3x2 mg tablets] or 8 mg [4x2 mg tablets]) will be administered per discussion with and approval from the Gilead medical monitor based on safety and tolerability of prior doses.

One dose of VRC07-523LS and 1 dose of CAP256V2LS will be administered sequentially by IV infusions on Day 7.

Participants will remain at the site for monitoring for 24 hours after Dose 1 of VES, for at least 8 hours after Dose 2 of VES, and for at least 4 hours after Dose 3 of VES. If participants experience significant influenza-like AEs (eg, moderate or severe pyrexia, chills, headache, myalgia, fatigue, malaise, joint pain) after the first 2 VES doses, or if dose is escalated to 8 mg, monitoring may be extended to > 4 hours for subsequent doses. For VRC07-523LS and CAP256V2LS, participants will remain on site for at least 8 hours after infusion on Day 7 for monitoring. If participants experience new or worsening flu-like symptoms, postdose safety monitoring should be extended.

Fasted status and food consumption will be checked prior to dosing.

Participants will continue to take their ART during this period (Days 0 to 28).

Sentinel Dosing:

Five participants will be enrolled first, to conduct visits and assessments up to Day 21. Upon review of the safety data and confirmation from an external DMC, up to a further 20 participants will be enrolled into Period 1.

Table 3. Period 1 Study Visits and Study Drug Administration

Period 1									
Week	-	-	-	1	-	-	2	3	4
Day	Baseline/0	1	2	7	8	9	14	21	28
VES Dose	1						2		3
VRC07-523LS and CAP256V2LS Dose				1					

ART (Days 0 to 28)

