All study visits are to be completed within \pm 3 days of the protocol-specified visit date (based on the Day 0 visit) except for the Day 7 visit, and study procedures are to be completed within \pm 2 hours of the protocol-specified time point.

At the Day 28 visit and prior to moving into Period 2, each participant will be assessed to determine whether the criteria to start ATI has been met as described in Section 6.3.3.

The following assessments are to be completed at every visit, unless otherwise specified.

- Symptom-directed physical examination
- Body weight
- Vital signs (blood pressure, pulse, respiration rate, oxygen saturation, and temperature) at:
 - Dose 1 of VES 24 hours after administration (**Day 1**)
 - VRC07-523LS and CAP256V2LS infusions prior to administration and at 1, 2, 4, and 8 hours after administration (**Day 7**)
 - Dose 2 of VES prior to administration and at 1, 2, 4 and 8 hours after administration (**Day 14**)
 - Dose 3 of VES prior to administration and at 1, 2 and 4 hours after administration (**Day 28**)
 - If the participant experiences new or worsening symptoms, evaluate for signs and symptoms of CRS, including vital signs
- Obtain blood samples for:
 - Plasma HIV-1 RNA (**Day 7 and each weekly visit thereafter**)
 - Plasma HIV-1 resistance testing (in case of viral rebound) to VRC07-523LS, CAP256V2LS, and baseline ART (**Day 7 and each weekly visit thereafter**)
 - Chemistry profile: ALP, AST, ALT, total bilirubin, direct and indirect bilirubin, total protein, albumin, CK, bicarbonate, BUN, calcium, chloride, creatinine, glucose, phosphorus, magnesium, potassium, sodium, uric acid (**all visits except Days 8 and 9**)
 - Hematology profile: CBC with differential and platelet count (**all visit days except Days 8 and 9**)
 - Creatinine clearance according to the Cockcroft-Gault formula (**all visits except Days 8 and 9**):

Female Estimated Creatinine Clearance = $[(140 - \text{age in years}) \times (\text{weight in kg})]/[72 \times (\text{serum creatinine in mg/dL})] \times 0.85$

- Anti-VRC07-523LS and anti-CAP256V2LS antibody profiling from serum (**Day 28**)
- HIV-specific antibody profiling using plasma (**Day 8**)
- Whole blood ISG mRNA panel (**Day 1**)
- Soluble proteins (cytokines, chemokines, and inflammatory markers) (**Days 1 and 8**)
- CD4+ and CD8+ T cell absolute count, percentage, and CD4/CD8 ratio (**Days 14 and 28**)
- PBMC sample for immune cell frequency, activation, and phenotyping (**Days 1 and 8**)

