6.3.3. ATI Eligibility Criteria

At the Day 28 visit and prior to the Period 2 Day 35 visit, participants will be assessed to determine whether the criteria necessary to begin ATI are met. All of the following criteria must be met for a participant to begin ATI (Period 2):

- Viral load < 50 copies/mL
- CD4+ T cell count > 400 cells/ μ L
- Negative urine pregnancy test
- Participant has received VRC07-523LS, CAP256V2LS, and at least 3 of the 10 scheduled doses of VES.
- Participant confirms agreement to request their partners to use condoms throughout the ATI period.

The initiation of ATI (Period 2) may be postponed for up to 4 weeks after the last VES dose for participants to meet the above requirements. If a participant develops any other acute event during this time that may require treatment before the participant starts the ATI (Period 2), the investigator should consult with the medical monitor. The investigator may delay the initiation of the ATI (Period 2), after consultation with the medical monitor, for up to a further 4 weeks if it is determined that the participant may proceed to ATI (Period 2) once the acute event has been treated successfully. The investigator should consult with the medical monitor to determine if repeat assessments should be performed to re-confirm the participant's eligibility for the ATI (Period 2).

Participants who do not meet the requirements for ATI (Period 2) will complete an ESDD visit within 3 days of informing the investigator/site and may undergo early discontinuation of study follow up and procedures as described in Section [6.9.2](#).

6.4. Treatment Assessments—Period 2

Participants will have up to 18 visits over 15 weeks. Doses 4 to 10 of VES will be administered orally on Day 42, Day 56, Day 70, Day 84, Day 98, Day 112, and Day 126.

For Doses 4 to 10, 6 mg [3x2 mg tablets] or 8 mg [4x2 mg tablets]) will be administered per discussion with and approval from the Gilead medical monitor based on safety and tolerability of prior doses.

Participants will remain at the site for monitoring for at least 4 hours after VES dosing. If participants experience significant influenza-like AEs (eg, moderate or severe pyrexia, chills, headache, myalgia, fatigue, malaise, joint pain) after the first 2 VES doses, monitoring may be extended to > 4 hours for subsequent doses. Fasted status and food consumption will be checked prior to dosing.

No ART will be administered and ATI will start from Day 35.

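### For a symptom-free participant at her first 8 mg vesatolimod dose, the protocol text requires no stay or vital signs beyond 4 hours, while schedule footnote l requires an 8-hour reading.

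*Protocol*

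**What the plan says.** **Dose.** Section 1.4.1 starts VES at 6 mg and allows 8 mg at the third administration (Day 28), "pending safety and tolerability of the 6 mg dose in each participant, with close safety monitoring". Section 5.3 is wider. It fixes 6 mg for Doses 1 and 2, then allows 6 or 8 mg "for Doses 3-10 per discussion with and approval from the Gilead medical monitor based on safety and tolerability of prior doses".

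**Stay.** Section 6.3 requires at least 8 hours on site after Dose 2 and at least 4 hours after Dose 3. Significant influenza-like events after the first two doses are one reason to extend; the other reads "or if dose is escalated to 8 mg, monitoring may be extended to > 4 hours for subsequent doses". Section 6.4 sets at least 4 hours for Doses 4 to 10. Its only trigger is significant influenza-like events "after the first 2 VES doses, monitoring may be extended to > 4 hours for subsequent doses"; 8 mg is not named.

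**Readings.** Section 6.3.2 has "Dose 3 of VES prior to administration and at 1, 2 and 4 hours after administration". Section 6.4.1 sets the same times for Doses 4 to 10, and Section 7.7.1 repeats both. Footnote l of Appendix 2a, copied in SAP Appendix 1, has "remaining VES Doses 2 to 10 at predose, then at 1, 2, 4, and 8 hours postdose".

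**Symptoms and staffing.** The synopsis (Period 1) and Section 6.3 say monitoring should be extended for new or worsening symptoms. Section 7.7.1 asks for CRS-trained staff and equipment on site for at least 4 to 8 hours after later VES doses.

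**Risk.** Section 1.5 reports: "One healthy volunteer who received 1 dose of VES 8 mg coadministered with EVM 250 mg experienced a Grade 3 SAE of CRS". The other three participants on that regimen had no serious event. It adds that giving VES while the study antibodies are detectable "may transiently increase the risk of inflammatory events".

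**The concern.** Section 1.4.1 promises close monitoring at escalation, but the operative sections do not turn that into a requirement. Without symptoms, a participant may leave 4 hours after her first 8 mg dose, half the stay required after her second 6 mg dose. A site could comply with the text and breach the footnote. Section 6 presents table and text together and gives neither precedence.

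Two things are at stake. The first is required protection at the one step where the dose rises. The second is how firmly CRS severity at 8 mg can be stated. In Table 7, hypotension or hypoxia separates Grade 2 CRS from Grade 1. An event starting after discharge can be recalled as flu-like symptoms, but it cannot be graded from readings unless the participant returns. SAP 7.1.8 reports these events by severity with no split by VES dose at onset. SAP 4.2.2 pools 8 mg use from the fourth dose onward, so a first 8 mg dose at Doses 4 to 10 is not identified.

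**Working it through.** The plan gives no figure to reproduce, so the check compares its rules.

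| VES dose | Level allowed (5.3) | Minimum stay (6.3, 6.4) | Post-dose readings, text (6.3.2, 6.4.1, 7.7.1) | Post-dose readings, footnote l |
|---|---|---|---|---|
| 2 | 6 mg | 8 h | 1, 2, 4, 8 h | 1, 2, 4, 8 h |
| 3 | 6 or 8 mg | 4 h; 8 mg may extend | 1, 2, 4 h | 1, 2, 4, 8 h |
| 4 to 10 | 6 or 8 mg | 4 h; 8 mg not named in 6.4 | 1, 2, 4 h | 1, 2, 4, 8 h |

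1. **Text against footnote.** They agree at Dose 2 and conflict at Doses 3 to 10, the only doses that can be 8 mg. The footnote sets a reading, not a stay.
2. **The 8 mg trigger.** In 6.3 and 7.7.1 it is permissive and applies to subsequent doses. That leaves unclear whether it covers the first 8 mg dose itself.
3. **Required observation.** Readings: 4 − 3 = 1 fewer at the first 8 mg dose than at Dose 2. Stay: 8 − 4 = 4 hours less, and 4/8 = 50%.
4. **Number of doses.** At most one first 8 mg dose per participant: 25 × 1 = 25. The escalation rate is not in the documents. Assumed rates of 20%, 40% and 100% give 5, 10 and 25.
5. **Precedent.** 1 of 4 = 25%. The exact (Clopper-Pearson) 95% lower limit solves 1 − (1 − p)⁴ = 0.025, giving 0.0063. The upper limit solves (1 − p)⁴ + 4p(1 − p)³ = 0.025, giving 0.8059. The interval is 0.6% to 80.6%.
6. **Antibody exposure.** Section 1.4.3 predicts VRC07-523LS above 20 µg/mL through Week 19. On the nominal schedule every possible 8 mg dose (Day 28 to Day 126, Week 18) falls within that time.
7. **Next scheduled vital signs, by the text.** After Dose 3: Day 42 − Day 28 = 14 days. Doses 4 to 9: also 14. Dose 10: Day 147 − Day 126 = 21. Adverse-event review and a symptom-directed examination come sooner, at Day 35 (7 days after Dose 3). Appendix 2a also has next-day visits after Doses 5 and 10 (Days 57 and 127).
8. **DMC.** Section 8.2.1.1 ties the one planned review to sentinel Day 21 visits. A participant's earliest 8 mg dose is Day 28, so the review is not designed to assess 8 mg.

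**The case against.** The step-down after Dose 2 is reasoned. Section 1.5 says VES-related events are more common after Doses 1 and 2 and proposes enhanced monitoring then, with adaptive monitoring afterwards. Dose 2 is also the first VES dose after the antibody infusions, so it is not a like-for-like comparator. Median VES Tmax was 1 to 3 hours (Section 1.2.4.1.1), inside the 4-hour stay. The precedent was same-day dosing with an Fc-enhanced antibody. Here VES and the antibodies are at least 7 days apart, the antibodies lack those mutations, and 8 mg follows two 6 mg doses and medical monitor approval. VES alone was generally tolerated up to 12 mg. Footnote l already schedules the 8-hour reading, and the SAP already plans dosing, adverse-event and vital-sign listings.

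Most of this stands, and it lowers the expected risk. It explains a general step-down, not what should happen when the dose rises, and none of it sets a stay or reading for a symptom-free participant at that point. A footnote that the text contradicts is not a dependable safeguard.

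Three stronger inferences are tempting but unsupported:

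- **That all monitoring after 4 hours is optional.** Symptoms direct longer monitoring (synopsis Period 1, Section 6.3) and a CRS evaluation with vital signs (Section 7.7.1); 4 hours is a minimum. But extension triggered by symptoms on site does not reach someone already discharged, and staff availability sets neither a stay nor a reading.
- **That the DMC could have seen no 8 mg dose.** It convenes once all five sentinel participants reach Day 21 or discontinue. With staggered enrollment an early one could have passed Day 28 by then.
- **That an 8-hour reading would have caught the earlier CRS event.** The documents do not give its onset time.

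**Conclusion.** The point holds for a symptom-free participant at her first 8 mg dose. The text requires 3 post-dose readings and a 4-hour stay and leaves extension for 8 mg optional; Section 6.4 does not mention 8 mg; and footnote l conflicts by requiring an 8-hour reading. The ceiling is 25 doses; 5 and 10 rest on assumed escalation rates. The precedent interval is too wide to estimate risk for this regimen and serves only to show that the hazard cannot be dismissed.

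A reader might extend the criticism to every dose from 3 to 10. For repeat doses at a level already tolerated, the mismatch is editorial only. No efficacy result, pharmacokinetic result or proportion with any treatment-emergent event changes. The documents do not prove 8 hours to be the right length. The case for it is that the schedule already lists that reading, Dose 2 already has that stay, and one rule would end a contradiction in a safety procedure. This is a change the sponsor should make, at moderate confidence.

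**What to change.** **Protocol (for reuse of this design).** In the synopsis and Sections 6.3, 6.3.2, 6.4, 6.4.1 and 7.7.1, require an 8-hour stay and an 8-hour vital-sign reading at each participant's first 8 mg dose, whatever its dose number. For VES Doses 2 to 10 and the antibodies, limit footnote l's 8-hour schedule to the antibody infusions, Dose 2 and the first 8 mg dose. Cost: a sentence in each place, a footnote correction, and up to 4 extra hours on site once per escalated participant.

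**This study.** SAP 2.3 treats the last participant's end-of-Period 3 visit as past, so dosing is complete. In the clinical study report:

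1. State which monitoring schedule the center followed.
2. List, for each first 8 mg dose, the dose number, the time of the last vital-sign reading, and any potential CRS or flu-like event with onset within 24 hours.
3. Keep all 8-hour readings at Doses 3 to 10 in the SAP 7.3 tables. Where they come only from extended stays, note n and the reason, because they are then a selected subset.
4. Word any statement on CRS severity at 8 mg to match the hours actually observed.

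Cost: one listing of at most 25 first 8 mg doses, a table note and a few sentences, from data already collected.
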